Appendix 1. United Nations Convention on the Rights of persons with disability

Article 1	Purpose
Article 2	Definitions
Article 3	General Principles
Article 4	General obligations
Article 5	Equality and non-discrimination
Article 6	Women with disabilities
Article 7	Children with disabilities
Article 8	Awareness-raising
Article 9	Accessibility
Article 10	Right to life
Article 11	Situations of risk and humanitarian emergencies
Article 12	Equal recognition before the law
Article 13	Access to justice
Article 14	Liberty and security
Article 15	Freedom of torture or cruel, inhuman or degrading treatment of punishment
Article 16	Freedom from exploitation, violence and abuse
Article 17	Protecting the integrity of the person
Article 18	Liberty of movement and nationality
Article 19	Living independently and being included in the community
Article 20	Personal mobility
Article 21	Freedom of expression and opinion, and access to information
Article 22	Respect for privacy
Article 23	Respect for home and the family
Article 24	Education
Article 25	Health
Article 26	Habilitation and rehabilitation
Article 27	Work and employment
Article 28	Adequate standard of living and social protection
Article 29	Participation in political and public life
Article 30	Participation in cultural life, recreation, leisure and sport
Article 31	Statistics and data collection
Article 32	International cooperation
Article 33	National implementation and monitoring
Article 34	Committee on the Rights of Persons with Disabilities
Article 35	Reports by States Parties
Article 26	Consideration of reports
Article 37	Cooperation between States Parties and the Committee
Article 38	Relationship of the Committee with other bodies
Article 39	Report of the Committee
Article 40	Conference of States Parties
Article 41	Depositary
Article 42	Signature
Article 43	Consent to be bound
Article 44	Regional integration organizations
Article 45	Entry into force
Article 46	Reservations
Article 47	Amendments
Article 48	Denunciation
Article 49	Accessible format
Article 50	Authentic texts

Appendix 2. WHO QualityRights e-training modules

Module	Topic	Contents
1	Human rights	This module provides information on what human rights are and the various international human rights documents. In this module, participants learn how different groups, including people with psychosocial disabilities, may be at higher risk of human rights violations and identify ways in which they can respect, protect, and fulfill human rights in their daily lives.
2	Mental health, disability, and human rights	This module provides information on the UN CRPD and, more specifically, on the human rights of persons with psychosocial disabilities. In this module, participants learn to view disability from a human rights perspective, to examine the barriers impeding the full inclusion of people with disabilities in society, and to identify ways to overcome these barriers. Mental health providers learn skills that will help them to support people with psychosocial disabilities to advocate for their rights.
3	The right to health and recovery	This module explains how a human rights-based approach is essential to the recovery of persons with psychosocial disabilities. In this module, participants have discussions about the concepts of mental health, well-being, and the right to health. They also learn the importance of ensuring that people with psychosocial disabilities are central actors in driving their care and recovery journey.
4	Legal capacity and the right to decide	In this module, particular relevance is given to the right to legal capacity and controversial topics such as the ban of substitute-decision making approaches and coercion, both in the mental health sector and in the general community. Emphasis on these problems is fundamental to overcome the division existing between mental health providers and people with psychosocial disabilities on these issues and make them work together for stopping the violations of the rights of the latter.
5	Free from coercion, violence, and abuse	This module provides information on how and why violence, coercion, and abuse occur in mental health settings and the general community. During this workshop, participants learn about the negative impact these practices have on people with psychosocial disabilities and examine the role of power relations in exacerbating violence, coercion, and abuses. Furthermore, participants learn about key strategies and approaches which have been shown to be effective in ending human rights violations within mental health services.

Appendix 3. Study settings

Facilities	Total number of staff	Total number of service users In-patients (per day)	# of inpatients units in the facility
ACCRA PSYCHIATRIC HOSPITAL	823	384	19
ANKAFUL PSYCHIATRIC HOSPITAL	483	146	6
PANTANG PSYCHIATRIC HOSPITAL	486	162	19

**Data provided by the Mental Health Authority, Ministry of Health (Ghana)*

Appendix 4. WHO novel coronavirus 2019 online trainings series

Module	Topic	Contents
1	Introduction to emerging respiratory viruses, including novel coronavirus (3 hours)	This module provides information on COVID-19 and other emerging respiratory viruses.
2	Infection Prevention and Control (IPC) for COVID-19 Virus (1 hour)	This module provides information on infection prevention and control, with a focus on COVID-19. In this module, participants learn how to identify COVID-19 infections and avoid further transmission of the virus in their facilities.
3	Health and safety briefing for respiratory diseases – ePROTECT (2 hours)	This module provides information on acute respiratory infections. In this module, participants learn basic hygiene measures to protect against acute respiratory infections, such as COVID-19.

4	COVID-19: How to put on and remove personal protective equipment (15 min)	This module provides information on the type of personal protective equipment health workers need to correctly protect themselves and on how to use this equipment.
5	Standard precautions: Hand hygiene (1 hour)	This module summarizes the WHO guidelines on hand hygiene and provides information on the associated tools and ideas for effective implementation.
6	Standard precautions: Waste management (1 hour)	This module provides information on waste management strategies to avoid transmission of COVID-19 in health facilities.
7	Standard precautions: Environmental cleaning and disinfection (1 hours)	This module provides information on environmental cleaning and disinfection. In this module, participants learn how cleaning and disinfection prevents contamination of the health care environment.
8	Occupational health and safety for health workers in the context of COVID-19 (1 hour)	This module provides information on occupational health and safety for health workers in the context of COVID-19. In this module, participants learn more about infectious risks to health and safety; physical risks to health and safety; psychosocial risks to health and safety; and basic occupational health and safety in health services.
9	Standard precautions: Injection safety and needle-stick injury management (2 hours)	In this module, participants learn about the causes of unsafe injection practices, how to safely give injections, and how to safely dispose of needles and other sharp instruments.
	Total 12 hours 15 min	

<https://www.who.int/emergencies/diseases/novel-coronavirus-2019/training/online-training>

Appendix 5. Schedule of enrollment, intervention, and assessments

	Recruitment	Pre-Intervention	Post-intervention	Follow-up (3 months)	Follow-up (6 months)
Eligibility criteria	x				
Informed consent	x		x	x	x
Allocation		x			
Socio-demographic questionnaires		x			
WHO's Knowledge about the rights of persons with psychosocial disabilities questionnaire		x	x	x	x
WHO's questionnaire on the attitudes towards people with psychosocial		x	x	x	x

disabilities as rights-holders					
Practices related to substitute-decision making and coercion scale		x		x	x
Abbreviated SREQ		x	x		
Information on the enrollment in the online WHO QualityRights training		x	x	x	
Information on the enrollment in other potential interventions		x	x	x	
Information on contacts with mental health professionals working in units allocated to a different arm		x	x	x	
Information on the satisfaction about the training			x		

Appendix 6. World Health Organization's Knowledge about the Rights of persons with psychosocial disabilities questionnaire

Please indicate if the following statements are True (T) or False (F).

		T	F
1	All 30 human rights within the Universal Declaration of Human Rights (UDHR) are needed to live a good life.		
2	The Universal Declaration of Human Rights (UDHR) is a law.		
3	Human rights can never be restricted.		
4	Violations of human rights can only be carried out by individuals, not by governments.		
5	The Convention on the Rights of People with Disabilities (CRPD) is a convention that protects the rights of all marginalized groups.		
6	According to the CRPD, people with dementia have the right to live in the community and to choose their living arrangements		
7	Informed consent is when a person's family members receive information about		

	different possible treatment options in order to make an informed decision.		
8	Advance plans/directives are documents made by health practitioners to plan in advance the treatment of people using the service.		
9	To promote legal capacity, family members, caregivers, and supporters should help people make decisions by explaining different options but should not assist in communicating decisions to others.		
10			
	Was intended to create new rights for people with disabilities		
	Adopts the medical and charity models of disability		
	Adopts the social and human rights models of disability		
	Is binding on countries which have ratified it		
11			
	Must show their ability to understand rights in order to claim them		
	Have the right to have attitudinal and environmental barriers removed		
	Cannot fully participate in society on an equal basis with others because of attitudinal and environmental barriers		
	Need treatment to 'fix' or heal them		
12			
	People cannot be detained based on the fact that they have a disability		
	People can be detained because they have a disability as long as other criteria such as dangerousness or medical necessity are also met		
	People with disabilities can only be deprived of liberty for the same reasons as any other person		
	Mental health laws can authorise people to be detained if they are diagnosed with a mental health condition and if they are perceived as dangerous		
13			
	Can be declined by the person		
	Requirements may vary throughout life		
	Should concern only complex decisions		
	Should increase throughout life		
14			
	Keep people safe		
	Are forms of coercion		
	Improve recovery if used correctly		
	Can cause harm		
15			
	User –led recovery and/or treatment plans		
	Healthcare provider-led recovery and/or treatment plans		
	Informed consent		
	Substitute-decision making		
16			
	Governments must make sure that people with disabilities are free from torture or cruel, inhuman or degrading treatment or punishment		
	The use of restraints is only allowed in cases where the service lacks adequate human resources		
	Countries must make laws to ensure that people with disabilities are protected from exploitation, violence and abuse in the home and in the community		
	There is no need to make laws to protect people with disabilities from exploitation, violence and abuse because the CRPD already ensures their protection		

Appendix 7. World Health Organization’s questionnaire on the attitudes towards people with psychosocial disabilities as rights-holders

Please indicate your level of agreement with the following statements.
Select only one option for each statement.

		Strongly Disagree	Disagree	Neutral	Agree	Strongly Agree
1.	Nothing can be improved within mental health services without additional resources.					
2.	The service environment has little to do with people's mental health and well-being.					
3.	People with dementia should always live in group homes where staff can take care of them					
4.	People with psychosocial disabilities/mental health conditions should not be hired in work requiring direct contact with the public.					
5.	Taking medication is the most important factor to help people with mental health conditions get better.					

		Strongly Disagree	Disagree	Neutral	Agree	Strongly Agree
6.	You can only inspire hope once a person is no longer experiencing symptoms					
7.	People using mental health services should be empowered to make their own decisions about their treatment.					
8.	Following advice of other people who have experienced mental health issues is too risky.					
9.	The opinions of health practitioners about care and treatment should carry more weight than those of a person with an intellectual disability.					
10.	It is acceptable to pressure people using mental health services to take treatment that they don't want.					
11.	Persons with mental health conditions should not be given important responsibilities.					
12.	When people experience a crisis, health practitioners or families should make decisions based on their ideas about what is best for them.					
13.	People with intellectual disabilities have the right to make their own decisions, even if I don't agree with them.					
14.	Controlling people using mental health services is necessary to maintain order.					
15.	The use of seclusion and restraint is needed if people using mental health services become threatening.					
16.	People at risk of harming themselves or others should be isolated in a locked room.					
17.	Involuntary admission does more harm than good.					

Appendix 8. The Practices related to substitute-decision making and coercion questionnaire.

Please indicate how many times in the last month you used the following strategies **within your psychiatric unit**.

Select only one option for each statement.

		Every day	A few times a week	Once a week	A few times a month	Once a month or less	A few times in the last three months	Never
1	I used seclusion (for instance, ordering or keeping service users in a locked room)							
2	I used physical restraints (for instance, using ties or other mechanical devices to restrain service users)							
3	I prescribed or administered a treatment although the service user did not want it							
4	I supported service users to write their recovery plan							
5	I informed service users about their rights (including their right to refuse treatment)							
6	I used chemical restraints (for instance, prescribing or administering an injection to calm the behavior of service users without their consent)							
7	I yelled or used verbal aggression to get service users to comply with requests							

For each statement, mark the box that most accurately reflects your response.

		A lot less than me	Less than me	As much as me	More than me	A lot more than me
8	Mental health professionals in my unit use seclusion and physical/chemical restraints					
9	Mental health professionals in my unit yell or use verbal aggression to get service users to comply with requests					
10	Mental health professionals in my unit prescribe or administer treatments to control the behavior of service users					
11	Mental health professionals in my unit respect the will and preferences of service users					
12	Mental health professionals in my unit use restraints to control unsettled situations in the ward					

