3.2.1.10. Collection of data and Assessment instruments

All the data will be collected through an online platform and made confidential according to the provisions that protect privacy in Europe (Articles 6 and 9 of EU Regulation No. 679) and Ghana (Data Protection Act, 2012).

- The **sociodemographic questionnaire** will include the following information:
 - I. Gender;
 - II. Age in years;
 - III. Educational attainment;
 - IV. Marital status;
 - V. Number of children;
 - VI. Religion;
 - VII. Profession;
 - VIII. Years working in a mental health service;
 - IX. Hospital and unit of work;
 - X. Region of residence;
 - XI. Main language;
 - XII. Family member(s) with a psychosocial disability;
 - XIII. Identification as “person with a psychosocial disability”.

In the case the WHO QualityRights intervention will be found to be not effective, these sociodemographic variables may be used to understand for which subgroups or under what circumstances the training did not work (although this work is outside the scope of the present proposal).

Primary outcomes

- The **World Health Organization’s Knowledge about the Rights of persons with psychosocial disabilities questionnaire** [Appendix 6] (16 items) was developed by WHO to assess knowledge about

the rights included in the UN CRPD. People with psychosocial disabilities had an active role in all the phases of the scale development.

- The **World Health Organization's questionnaire on the attitudes towards people with psychosocial disabilities as rights-holders** [Appendix 7] (17 items) was developed by WHO and includes three subscales: attitudes towards institutionalization and living independently in the community; attitudes toward mandatory treatment and coercion; attitudes toward people with psychosocial disabilities as decision-makers. People with psychosocial disabilities had an active role in all the phases of the scale development.

Secondary outcomes

- The **Practices related to substitute-decision making and coercion scale** [Appendix 8] (12 items) is a scale developed to measure the use of substitute-decision making and coercive practices in mental health units.

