Since the data are continuous and longitudinal, linear mixed-effects (LME) regression models will be used to estimate average intervention effects while considering the shared variance of repeated measures and the clustered variance. Correlations arising from repeated measures will be accounted for by specifying an autoregressive covariance structure. Each outcome will be analyzed separately using LME. Time, intervention arm, and their interaction will be included in the model as fixed effects, while participants will be evaluated as random effects. Time will be entered as a categorical variable with levels corresponding to post-training and 3 AND 6 months. The effect of the intervention on the outcomes will be captured by the interaction between intervention and time, which will assess the mean difference between the intervention arms (QR e-training vs. control) in changes of outcomes over time within each group. Effect sizes will be reported as mean differences for each time point and intervention arm, with 95% confidence intervals.

(Random intercept with two group-level covariates and interaction).

Level 1:

$$Y_{ij} = b_{0j} + \varepsilon_{ij}$$

Level 2:

$$b_{0j} = \beta_{00} + \beta_{01}w_j + \beta_{02}t_j + \beta_{03}w_jt_j + b_{0j}^*$$

Combined:

$$Y_{ij} = \beta_{00} + \beta_{01}w_j + \beta_{02}t_j + \beta_{03}w_jt_j + b_{0j}^* + \varepsilon_{ij}$$

- Y_{ij} = attitudes
- β_{00} = "average mean" of units mean attitudes

- b_{0j}^* = difference between specific unit mean attitudes and “average mean” of units mean attitudes
- ε_{ij} = difference between individual attitudes and unit mean attitudes
- t_j = time (3 = at 6 months; 2 = at 3 months; 1 = post – training; 0 baseline)
- w_j = (1 = QR training; 0 control)
- β_{02} = regression coefficient for time
- β_{01} = regression coefficient for unit average attitudes when assigned to QR
- β_{03} = regression coefficient for the interaction of time and intervention

3.1.2.4 Secondary analyses.

Secondary outcomes will be the change in practices and experiences related to substitute-decision making and coercion. The change in practices will be evaluated at three months and six months, while the change in experiences will be evaluated both post-intervention and at three months and six months. These changes will be evaluated using the same methodology already described for the main analyses.

References

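### The practices questionnaire mixes a one-month and a three-month recall window, and 5 of its 12 items compare colleagues with the respondent instead of recording how much coercion is used

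*Protocol*

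**What the plan says.** Section 3.2.1.10 of the protocol lists the 12-item practices instrument as a secondary outcome. It says that it "is a scale developed to measure the use of substitute-decision making and coercive practices in mental health units". Section 3.1.2.4 states: "The change in practices will be evaluated at three months and six months". On the method it adds: "These changes will be evaluated using the same methodology already described for the main analyses". That method is the linear mixed model for continuous outcomes.

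Appendix 8 prints the instrument in two blocks.

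- **Items 1-7** concern the respondent's own conduct. The stem is "Please indicate how many times in the last month you used the following strategies". There are seven options, from every day down to never. The two just above never are "Once a month or less" and then "A few times in the last three months". Items 4 and 5 describe supportive conduct, for example "I supported service users to write their recovery plan"; the other five describe coercive conduct.
- **Items 8-12** concern colleagues, for example "Mental health professionals in my unit use seclusion and physical/chemical restraints". All five options are comparisons with the respondent, from far less to far more. Item 11, on respecting service users' wishes, runs in the opposite direction to the other four.

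The protocol gives no scoring rule, item direction or weighting for this instrument. Section 3.2.1.10 leaves its psychometric evaluation to a separate document.

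**The concern.** There are two separate faults in how the answers are collected.

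First, the stem and one answer option use different recall windows, and that option overlaps its neighbour. The ambiguity sits at the low-use end, which is where a successful training should move people.

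Second, a comparison with oneself is not a measure of use. If a unit's staff all reduce coercion equally, the honest answers to items 8-12 do not change. If only the respondent changes, or only the colleagues do, the answers shift. Whether that shift counts as better or worse depends on a scoring choice that the protocol does not state.

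Section 1 calls a change in practices the ultimate goal. This is the only instrument that asks about conduct, since the seclusion and restraint questionnaire covers emotional and ethical experiences. An unclear result here would leave the behavioural question open.

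**Working it through.** The protocol states no sample size, power or score for this instrument. Its 126 per arm is based on the attitudes questionnaire (section 3.2.1.14), so there is no figure to reproduce for this outcome.

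**Recall options.** Rank the three lowest options as printed: never = 0, the three-month option = 1, the once-a-month-or-less option = 2.

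| True behaviour | Boxes that can truthfully be ticked |
|---|---|
| Two uses in three months, none in the last month | 0 (by the stem), 1 (by its label), 2 (as a rate) |
| One use in three months, not in the last month | 0 (by the stem), 2 (as a rate) |

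The first person fits three boxes and the second fits two. If the first ticks the three-month option (rank 1) and later, after falling to one use, ticks the rate option (rank 2), a real decrease raises the item by 2 - 1 = 1.

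**Items 8-12 in a sum.** This is an illustration under an assumed rule, because none is stated. Score items 1-7 from 0 to 6 with items 4 and 5 reversed, and items 8-12 from 0 to 4 with item 11 set against the other four. Higher means more coercion.

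- Range: 7 × 6 + 5 × 4 = 42 + 20 = 62. Items 8-12 hold 20/62 = 32% of the points.
- Start: every frequency item at 3 and every comparison item at the midpoint of 2, so 7 × 3 + 5 × 2 = 31.

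Each change below is one category or one box. Direction X scores colleagues doing more coercion than the respondent as worse; direction Y scores it as better.

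| Change | Total, direction X | Total, direction Y |
|---|---|---|
| A. Respondent falls on items 1, 2, 3, 6, 7; colleagues unchanged | 31 - 5 + 5 = 31 | 31 - 5 - 5 = 21 |
| B. Respondent falls on items 1, 2, 6 only; items 8, 10, 11, 12 shift and item 9 (verbal aggression) does not | 31 - 3 + 4 = 32 | 31 - 3 - 4 = 24 |
| C. Whole unit falls equally on items 1, 2, 3, 6, 7 | 31 - 5 + 0 = 26 | 31 - 5 + 0 = 26 |
| D. Colleagues fall; respondent unchanged | 31 + 0 - 5 = 26 | 31 + 0 + 5 = 36 |

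Under X, the respondent's own improvement is cancelled in A and shows as a slight worsening in B. Under Y, those two cases move the right way, but an improvement among colleagues shows as a worsening in D. Neither direction turns items 8-12 into an amount of coercion. In C the total still falls, through items 1-7 alone.

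**The case against.** The strongest reply is that nothing in the protocol says the 12 items are summed. The term total score is used for the attitudes questionnaire, not for this one. The two blocks have separate instructions and formats, which suits separate scoring at least as well as a sum. A scoring rule commonly sits in the analysis plan or, here, could sit in the deferred psychometric document. All of this stands: the absence of a scoring rule is not itself a fault, and every total above is an assumption.

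It also stands that the recall overlap touches two adjacent options at the rare-use end, in both arms and at every assessment of this scale. Much of its effect may be noise. Likewise, dropping items 8-12 removes the instrument's only questions about colleagues, although the scale is described as covering practice in units.

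The reply does not answer the core of the point. No later scoring document can recover the intended meaning of answers given on overlapping options with two recall windows, or convert a comparison into a frequency.

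Three stronger readings are tempting but unsupported.

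- *That the score will stay flat or worsen when coercion falls.* This needs a sum, a particular direction and unequal change between respondent and colleagues. Rows A and B under Y, and row C under both, show the total falling as it should.
- *That the loss can be put as a percentage.* For example, √(7/12) = 0.76 would suggest a 24% smaller standardised effect if items 8-12 did not move. That assumes independent items of equal variance. The protocol gives no variances or correlations, and the two blocks have different ranges.
- *That respondents will mostly be judging untrained colleagues.* Recruitment is of a random sample within each unit, averaging 2 × 126 / 28 = 9. Appendix 3 gives (823 + 483 + 486) / 44 = 1792 / 44, about 41 staff per inpatient unit, but that counts all staff in hospitals that also run outpatient units. The number of eligible professionals per unit is not given.

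**Conclusion.** The point holds for the instrument as printed. The recall window of items 1-7 contradicts one of their own answer options, and the order of the options can reverse at low use. Items 8-12 measure relative standing, yet they are presented as part of one scale of use whose change is to be analysed.

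That a combined score could dilute, offset or reverse a real change is conditional on a sum and on a scoring direction. The documents do not allow its size to be derived.

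The consequence is confined to one secondary outcome; the primary outcomes and the sample size are unaffected. It merits correction before baseline because faulty answer options cannot be fully repaired after collection.

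**What to change.** Before baseline:

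1. Replace the two overlapping options with a single option that lies inside the last-month window and below the next more frequent one, and limit the last option to never in the last month.
2. Define the change-in-practices outcome on the own-use items 1-7, with items 4 and 5 reversed so that all point the same way.
3. Report items 8-12 separately as a peer comparison, outside the change score. If unit-level practice is to stay in the outcome, reword them to ask for absolute frequency.

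The cost is a small questionnaire edit and a few lines of scoring text. The downside is a shorter score with narrower unit-level content, unless items 8-12 are reworded.

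If the questionnaire has already been fielded, score the two overlapping options as one category and say that this is only a partial repair. It removes the order reversal between those two options but does not restore a last-month window: it pools people with use in the last month and people whose use was earlier, and the never option stays ambiguous.
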